1. INTRODUCTION

1.1. Overview

APP13007 is an ophthalmic nanosuspension that is prepared by dispersing nanomilled clobetasol propionate (CP), a corticosteroid, with a mixture of excipients in a multi-dose preserved aqueous formulation. [REDACTED]

[REDACTED]

[REDACTED]

[REDACTED]

1.2. Background

1.2.1. Clobetasol Propionate

Corticosteroids regulate cellular signaling, immune function, inflammation and protein synthesis, and like other corticosteroids, CP has anti-inflammatory and vasoconstrictive properties. The mechanism of the anti-inflammatory activity of CP is unclear, but it is thought to act by inducing lipocortins, proteins that inhibit phospholipase A2, an enzyme that releases arachidonic acid from membrane phospholipids. By inhibiting phospholipase A2, lipocortins control the biosynthesis of potent mediators of inflammation such as prostaglandins and leukotrienes.

CP is an analog of prednisolone with a very high degree of activity at the glucocorticoid receptor and only slight degree of mineralocorticoid activity (Clobex® Product Insert 2018). It is reported to be the most potent corticosteroid in terms of binding affinity to the glucocorticoid receptor and resulting pharmacological effects (Olsen and Cornell 1986, Jacob and Steele 2006). CP has been used in dermal applications including ointments, creams and shampoos, where its efficacy and safety has been well-established (Clobex® Product Insert 2018; Temovate® Product Insert 2000; Olsen 1986; Hengge 2006; Feldman 2009).

1.2.2. Pain and Inflammation Following Cataract Surgery

Despite modern advances in surgical technique, trauma that occurs during cataract removal and intraocular lens (IOL) placement regularly leads to some degree of inflammation. The cellular damage on the surface of the cornea activates an inflammatory process that manifests initially as hyperemia, corneal edema, and increased anterior chamber cells and flare. More serious complications such as corneal edema, increases in intraocular pressure (IOP), cystoid macular edema (CME), and posterior capsule opacification (PCO) may result if the inflammatory process is not managed appropriately (J.L. 1978, Apple, Solomon et al. 1992). For this purpose, a 2-week post-cataract surgery regimen of anti-inflammatory agents (such as corticosteroids) is typically prescribed because it reverses inflammation, pain and discomfort and reduces the risk of further complications. When administered at the time of surgery and during the immediate

postoperative period, corticosteroids can reverse the clinical and non-clinical manifestations of inflammation (Leopold 1985, Aptel, Colin et al. 2017).

1.2.3. Rationale for Development of APP13007

Topical ocular administration of corticosteroids is a well-established therapy for the treatment of inflammation and pain after ocular surgery (Aptel, Colin et al. 2017), and several marketed products are currently available that contain active ingredients such as dexamethasone, prednisolone, loteprednol etabonate and difluprednate.

[figure not shown]
CP, reportedly the most potent steroid and classified as a superpotent corticosteroid in the US, has been used extensively in dermatological applications (Olsen and Cornell 1986, Jacob and Steele 2006, Feldman and Yentzer 2009). Of note, CP has been used for over 30 years in the US, Europe and Japan to treat the inflammatory and pruritic manifestations of corticosteroid responsive dermatoses such as psoriasis, eczema and atopic dermatitis. CP has not been previously developed for ophthalmic use, presumably due to its lack of aqueous solubility. Nevertheless, given its increased potency, an aqueous ophthalmic formulation of CP has the potential to produce rapid clearance of anterior chamber cells (ACC), return of visual acuity and relief of pain after ocular surgery, surpassing the effectiveness of corticosteroids currently on the market.

APP13007 is an ophthalmic nanosuspension that is prepared by dispersing nanomilled CP with a mixture of excipients. The proprietary nanomilling technology allows CP to be formulated as an aqueous suspension. This suspension of CP nanoparticles in APP13007 is designed to promote efficient penetration of CP into the eye upon ocular surface instillation, thus delivering therapeutically relevant concentrations of CP to the target tissues within the eye.

1.3. Nonclinical Studies

Multiple nonclinical pharmacology, pharmacokinetics, and toxicology studies have been conducted with various formulations of APP13007, and these are summarized in the APP13007 Investigator Brochure.

1.3.1. Primary Pharmacology

[REDACTED]

[REDACTED]

1.3.2. Pharmacokinetics

[REDACTED]

The planned dosing regimen for this clinical study of APP13007 is one drop (not more than 50 μ L) of 0.05% and 0.1% APP13007 given once or twice daily for 21 days. [REDACTED]
[REDACTED]
[REDACTED]
[REDACTED]
[REDACTED]

[REDACTED]

In summary, the systemic exposure to CP after ocular instillation of APP13007 is expected to be minimal and thus the associated systemic safety profile in humans is not expected to differ significantly from that previously demonstrated for dermal products containing CP.

1.3.3. Toxicology

Data from non-GLP and 14-day and 28-day Good Laboratory Practice (GLP) toxicity studies of APP13007 are summarized in the APP13007 Investigator Brochure.

[REDACTED]

The data from repeat dose toxicology studies do not identify any unacceptable risk for human subjects. With respect to systemic effects, the toxicology studies suggest that potential systemic effects in human subjects with ocular instillations of APP13007 are those typical of corticosteroids in general and that have been seen with approved dermal CP products, such as Temovate® and Clobex® (Temovate® 2000, Clobex® 2018). [REDACTED]

[REDACTED]

[REDACTED]

[REDACTED]

1.4. Risk/Benefit Assessment

1.4.1. Potential Risks

Potential Risks Anticipated Based on Results from the GLP Rabbit Toxicology Studies with APP13007

As summarized in Section 1.3.3, there were no adverse ocular findings follow ocular instillation of APP13007, [REDACTED]

[REDACTED] the proposed dosing regimens for APP13007 in this study is expected to result in systemic exposure to CP not more than that seen with dermal CP products, and the associated systemic safety profile in humans is not expected to differ significantly from that previously demonstrated for dermal products containing CP.

Potential Risks Associated with the Use of CP in the Treatment of Corticosteroid-Responsive Dermatoses

There is extensive experience with CP in the treatment of inflammatory and pruritic manifestations of corticosteroid-responsive dermatoses, where its safety and anti-inflammatory profile has been well defined (Olsen and Cornell 1986, Hengge, Ruzicka et al. 2006, Feldman and Yentzer 2009). The majority of clinical trials of CP have been up to 2-4 weeks in duration in the two most prevalent steroid-responsive skin disorders, eczema and psoriasis (Feldman and Yentzer 2009).

This is the first clinical study investigating the safety, tolerability and preliminary efficacy of an [REDACTED] APP13007, which is being developed for the treatment of inflammation and pain after ocular surgery.

Potential Non-Ocular Risks:

- Hypothalamic-Pituitary-Adrenal (HPA) Axis Suppression: Systemic absorption of topical corticosteroids can produce reversible HPA axis suppression and reduction of circulating cortisol concentration with the potential for glucocorticoid insufficiency after withdrawal from treatment. Recovery of HPA axis function is generally prompt upon discontinuation of topical corticosteroids.

Cushing's syndrome, hyperglycemia, and unmasking of latent diabetes mellitus can also result from systemic absorption of topical corticosteroids. Use of more than one corticosteroid-containing product at the same time may increase the total systemic corticosteroid exposure.

- Skin: Allergic contact dermatitis may occur. If irritation develops, APP13007 should be discontinued and appropriate therapy instituted. With prolonged use, local skin reactions

may include atrophy, striae, telangiectasias, burning, itching, irritation, dryness, acneiform eruptions, hypopigmentation, hypertrichosis, secondary infection and miliaria.

- Pregnancy and Nursing Mothers: [Note: females of child-bearing potential as well as pregnant and/or nursing mothers are excluded from participation in this study.] Corticosteroids have been shown to be teratogenic in laboratory animals when administered systemically at relatively low dosage levels (Pregnancy Category C). When administered subcutaneously, CP was a significant teratogen in both the rabbit and mouse.

Systemically administered corticosteroids appear in human milk and could suppress growth, interfere with endogenous corticosteroid production, or cause other untoward effects. It is not known whether ocular administration of APP13007 could result in sufficient systemic absorption of CP to produce detectable concentrations in human milk.

[REDACTED] plasma CP concentrations in human subjects after ocular instillation of one drop of APP13007 are expected to be lower than that observed in human subjects after dermal application of CP-containing products.

Potential ocular risks are summarized below.

Potential Class-Related Ocular Risks Associated with Corticosteroid Therapies for the Treatment of Ocular Inflammation and Pain after Ocular Surgery

[figure not shown]
The active ingredient in APP13007, [REDACTED] has the following anticipated ocular risks associated with the corticosteroid class:

- Intraocular pressure (IOP) increase – prolonged use may result in glaucoma with damage to the optic nerve, defects in visual acuity and field of vision.
- Cataracts – Prolonged use [REDACTED] may result in posterior subcapsular cataract formation in the non-operated eye.
- Delayed healing – Use [REDACTED] after cataract surgery may delay healing and increase the incidence of bleb formation. In those diseases causing thinning of the cornea or sclera, perforations have been known to occur with the use of topical corticosteroids.
- Risk of Infection
 - Bacterial infections – Prolonged use [REDACTED] may suppress the host immune response and thus increase the hazard of secondary ocular infections. In acute purulent conditions, corticosteroids may mask infection or enhance existing infection.
 - Viral infections – Use of ocular corticosteroids may prolong the course and may exacerbate the severity of many viral infections of the eye (including herpes simplex).
 - Fungal Infections – Fungal infections of the cornea are particularly prone to develop coincidentally with long-term local corticosteroid application. Fungus invasion must

be considered in any persistent corneal ulceration while a subject is participating in this clinical trial.

In clinical studies evaluating the use of corticosteroids after ocular surgery, ocular adverse reactions that occurred in 5% to 15% of subjects included corneal edema, ciliary and conjunctival hyperemia, eye pain, photophobia, posterior capsule opacification, anterior chamber cells, anterior chamber flare, conjunctival edema, and blepharitis. Other ocular adverse reactions occurring in 1% to 5% of subjects included reduced visual acuity, punctate keratitis, eye inflammation, and iritis. Ocular adverse reactions occurring in less than 1% of subjects included application site discomfort or irritation, corneal pigmentation and striae, episcleritis, eye pruritus, eyelid irritation and crusting, foreign body sensation, increased lacrimation, macular edema, sclera hyperemia, and uveitis. Most of these reactions may have been the consequence of the surgical procedure.

Potential Risks Associated with the APP13007 Formulation

1.4.1.1. Risk Mitigation Plan

Given the potential risks noted above, a risk mitigation plan will be used to mitigate risks for subjects enrolled into the study. The Risk Mitigation Plan is shown in Table 3.

1.4.1.2. Contraindications

APP13007, as with other corticosteroids, is contraindicated in the presence of active viral diseases of the cornea and conjunctiva including epithelial herpes simplex keratitis (dendritic keratitis), vaccinia, and varicella, and also in subjects with mycobacterial infection of the eye and fungal diseases of ocular structures.

1.4.2. Potential Benefits

Topical ocular administration of corticosteroids is a well-established therapy for the treatment of inflammation and pain after ocular surgery, with multiple marketed products currently available that utilize corticosteroids as the active ingredient such as dexamethasone (Maxidex®), prednisolone (PredForte®), loteprednol etabonate (Lotemax®, Inveltys™, and difluprednate (Durezol®). As summarized in the Product Inserts for Lotemax® and Durezol®, in clinical trials post ocular surgery, approximately 20-30% of subjects had clearing of anterior chamber cells and approximately 60-80% of subjects were pain free by Day 8 of treatment. Furthermore, approximately 40% of patients had clearing of anterior chamber cells and approximately 60% of patients were pain free after 15 days of treatment with Durezol®. In all clinical trials, corticosteroid therapies were dosed at a frequency of twice daily or more frequently. Thus, a more potent corticosteroid such as CP with a reduced dosing frequency may be advantageous over current therapies used to treat inflammation and pain following ocular surgery.

This is the first time that APP13007 will be administered to humans, therefore any potential direct benefit to subjects enrolled into this study is based on results of nonclinical pharmacology studies. However, given the potency of CP and known ocular use of corticosteroids, it is likely that subjects enrolled into this study and randomized to APP13007 may experience a reduction in inflammation and pain following cataract surgery.

It is known from clinical trials of products for the treatment of inflammation and pain after ocular surgery that a proportion of subjects randomized to placebo improve in the days following surgery (Lotemax® Product Insert 2018; Durezol® Product Insert 2017). Thus, there may be a marginal benefit to some of the subjects enrolled into the study that are randomized to placebo.

1.4.3. Assessment of Potential Risks and Benefits

This is a placebo-controlled study in which subjects will be randomized 1:1 to APP13007 or matching vehicle placebo. Subjects randomized to APP13007 may benefit from the treatment by reduction in inflammation and pain, while the risks associated with APP13007 treatment are

[REDACTED]

Subjects randomized to placebo are not expected to benefit from the study treatment, but a proportion of subjects receiving placebo may improve in the days following surgery. Furthermore, the risks to subjects randomized to placebo in this study are mitigated as much as possible. Specifically, the protocol contains instructions for careful monitoring of safety and efficacy endpoints during the trial to identify subjects who show minimal improvement or worsening of the clinical conditions so that appropriate mitigation steps can be taken, including, but not limited to, withdrawal from study treatment and commencement of appropriate rescue procedures.

Overall, the risk:benefit analysis supports the evaluation of 0.05% and 0.1% strengths of APP13007 and matching vehicle placebos administered BID or QD for up to 21 days after cataract surgery.

Table 3: Risk Mitigation Plan

Potential Risk	Management	Comments
Risk Associated with Lack of Efficacy		
Minimal reduction or worsening of inflammation and pain endpoints or other factors suggesting lack of efficacy	
Inflammation and pain endpoints will be monitored during the study.
 
Guidance criteria and procedures for the rescue of subjects are provided in Section 9 of this protocol.
	No dose modification is allowed in this study, but study drugs may be discontinued if there is substantial evidence indicating lack of efficacy of a dose regimen of APP13007.
Risk Associated with Unexpected Safety Events		
Unexpected safety events	
Safety endpoints will be monitored during the trial.
 
The Investigator will discuss unexpected safety events with the Study Medical Monitor who will then discuss unexpected safety events with the Sponsor to determine whether study drug should be stopped and rescue procedures commenced.
	
The toxicology studies with APP13007 indicate that there is a low risk of ocular toxicity. While the risks of systemic exposure to CP following dermal/topical administration are well characterized, aqueous formulations of CP have not been dosed to the human eye before.
 
Therefore, the Investigator should be alert to the possibility that unexpected safety events may occur. The list of expected safety events is including in Section 1.4.1 and in the APP13007 Investigator's Brochure.

Risks Associated with the Corticosteroid Class		
Intraocular pressure (IOP) increase	
IOP will be monitored during the study.
 
The protocol excludes participation of subjects who may be at increased risk of steroid-induced IOP increase, eg. subjects with a history of raised IOP and subjects with IOP >30 mmHg at the POD1 pre-randomization assessment.
	
The toxicology studies with APP13007 indicate that there is a low risk of IOP increase during the 21 days of treatment.
 
Prolonged use of CP may result in glaucoma with damage to the optic nerve, defects in visual acuity and fields of vision.
 
An IOP ≥ 30 mmHg after randomization should be reported as an AE.

Potential Risk	Management	Comments
	
Section 9 includes stopping criteria for study drug due to IOP increase and criteria for initiation of IOP-lowering medication.
 
After Randomization, the management of IOP > 30 mmHg or IOP ≥ 24 mmHg AND an IOP increase ≥ 10 mmHg from pre-dose baseline is described in Section 9.4.2.
	
An IOP ≥ 24 mmHg AND an IOP increase ≥ 10 mmHg from pre-dose baseline should be reported as an AE.

Cataracts	
The lens structure and posterior capsular opacification (POC) in the study eye will be monitored at each clinic visit throughout the study. The lens in the non-operated eye will be evaluated at Screening, EOS and Early Termination visits.
	
Based on data from studies of dermal products of CP, use of APP13007 may result in posterior subcapsular cataract formation in the non-operated eye. While the risk is likely to be small, this cannot be quantified because the extent of CP systemic exposure in humans following ocular instillation of APP13007 is not known.

Delayed Healing	
Subjects with thinning of the cornea or sclera are excluded because of the greater risk of perforations with the use of topical steroids.
 
Protocol includes stopping criteria for study drug if the Investigator, in consultation with the Study Medical Monitor, is concerned about delayed healing.
	
Use of APP13007 may delay healing after cataract surgery and increase the incidence of bleb formation.

Risk of Infection	
Subjects with on-going ocular bacterial, viral or fungal infections are excluded from the study.
 
Ocular infections occurring during the study should be assessed and treated appropriately.
 
The Investigator should discuss with the Study Medical Monitor whether to stop study drug if ocular infection occurs.
	
Use of APP13007 may suppress the host immune response and increase the hazard of ocular infections. This risk is likely to be low based on potential low systemic CP exposure and data from studies of other steroids products approved for the treatment of inflammation and pain after ocular surgery.

Hypothalamic-Pituitary-Adrenal	Monitor for symptoms and signs of reduced adrenal function	Systemic absorption of topical corticosteroids can produce

Potential Risk	Management	Comments
Axis (HPA) Suppression	
(including fatigue, muscle weakness, loss of appetite and weight, abdominal pain, nausea and diarrhea, low blood pressure, depression and irritability, salt craving and hypoglycemia).
 
The Investigator should discuss with the Study Medical Monitor who will then discuss with the Sponsor whether to stop study drug.
	
reversible HPA axis suppression with the potential for glucocorticoid insufficiency after withdrawal from treatment.
 
Investigators should be aware that the symptoms and signs of reduced adrenal function can be nonspecific and they should remain alert to the possibility that this may occur.
 
Recovery of adrenal function is generally prompt upon discontinuation of topical corticosteroids.

Effects related to excessive corticosteroid pharmacology	
Monitor for symptoms and signs of excess corticosteroid pharmacology such as Cushing's syndrome, hyperglycemia, and unmasking of latent diabetes mellitus.
 
The Investigator should discuss with the Study Medical Monitor who will then discuss with the Sponsor whether to stop study drug.
	
These effects have been reported after dermal use of CP and result from systemic absorption of topical CP.
 
While the risk is likely to be small, this cannot be quantified because the extent of systemic exposure in humans following ocular instillation of APP13007 is not known.

Pregnancy Category C/Fetal effects	Women of child-bearing potential as well as pregnant and/or nursing mothers are excluded from the study	Corticosteroids are known teratogens in laboratory animals when administered systemically at relatively low dosage levels.
Skin Irritation	
If irritation develops appropriate therapy should be instituted.
 
The Investigator should notify the Study Medical Monitor in advance if study drug is going to be stopped.
	
Allergic contact dermatitis may occur with CP.
 
Other skin reactions have been described with topical dermal products (Section 1.4.1)

Other Potential Risks		

Potential Risk	Management	Comments
	seminal vesicles were seen at all dose levels. [REDACTED]	
Hypersensitivity Reactions	Subjects are excluded from the study if they have a history of hypersensitivity to CP, [REDACTED] If hypersensitivity reaction occurs, the Investigator should discuss with the Study Medical Monitor who will then discuss with the Sponsor Medical Monitor whether to stop study drug.	
Adverse reactions reported in clinical studies evaluating the use of corticosteroids after ocular surgery	Most of these adverse reactions may have been the consequence of the surgical procedure and should be managed according to standard-of-care procedures.	Ocular adverse reactions reported are summarized in Section 1.4.1.

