8.2. Definition of Serious Adverse Events (SAEs)

An AE is considered "serious" if the event results in any of the following outcomes:

- death,
- a life-threatening adverse event (i.e. the subject is, in the view of the investigator, at immediate risk of death from the AE as it occurs),
- inpatient hospitalization or prolongation of existing hospitalization,
- a persistent or significant incapacity or substantial disruption of the ability to conduct normal life functions, or
- a congenital anomaly/birth defect.

Important medical events that may not result in death, but may be life-threatening, or require hospitalization may be considered serious when, based upon appropriate medical judgment, they may jeopardize the participant and may require medical or surgical intervention to prevent one of the outcomes listed in this definition. Examples of such medical events include allergic bronchospasm requiring intensive treatment in an emergency room or at home, blood dyscrasias or convulsions that do not result in inpatient hospitalization, or the development of drug dependency or drug abuse.

A suspected unexpected serious adverse reaction (SUSAR) is defined as a serious adverse reaction that is not listed in the APP13007 Investigator's Brochure or is not listed at the specificity or severity that has been observed, or that is mentioned in the APP13007 Investigator's Brochure as occurring with a class of drugs or as anticipated from the pharmacological properties of the study drug, but is not specifically mentioned as occurring with the particular drug under investigation. (See Section 8.7.2).

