8.3.3. Expectedness

An AE or a suspected adverse event (SAR) is considered "unexpected" if it is not listed in the APP13007 Investigator's Brochure or is not listed at the specificity or severity that has been observed. Expected events for APP13007 administration include those events described in Section 1.4.1 and the APP13007 Investigator's Brochure.

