8.7. Serious Adverse Event Reporting

8.7.1. Reporting Requirements

It is the responsibility of the Investigators or their designees to report any event of this nature to the Sponsor or a designee within 24 hours of the event being brought to the Investigators' or their staffs' attention. It is also the responsibility of the Investigator to report all SAEs reported at their site to the IRB, as required. The Investigator should make every attempt to follow all SAEs to resolution.

All SAEs have to be reported, whether or not considered causally related to the investigational drug product, or to the study procedure(s). All SAEs will be recorded in the eCRF. SAEs will be recorded from the time of informed consent.

All Serious Adverse Events (SAE) must be reported, whether or not considered related to the study drug, on a separate SAE Report Form. All SAEs will also be recorded in the eCRF. The Sponsor will be responsible for reporting all SAEs to regulatory authorities and ethics committees (see NOTE below) in accordance with ICH Good Clinical Practice and local regulations. As soon as the Investigator is aware of a potential SAE he/she should contact [REDACTED] by fax or e-mail and in any case *no later than 24 hours* after the knowledge of such a case. At the time of initial reporting the Investigator must provide as a minimum requirement, subject number, birth date, description of the SAE and a preliminary assessment of causality.

For fatal or life-threatening adverse events where important or relevant information is missing, active follow-up is undertaken immediately. Investigators or other site personnel inform the Study Medical Monitor, the Sponsor, and the CRO for Study Management and Monitoring of any follow-up information on a previously reported SAE immediately but no later than within 24 hours of when the Investigator becomes aware of it. The Study Medical Monitor or Sponsor Medical Monitor will advise the Investigator/study site personnel how to proceed.

The SAE reporting procedures are detailed in the study specific Safety Management Plan. This plan is an agreement between the Sponsor, the CRO for Study Management and Monitoring and Drug Safety Navigator.

NOTE: If an unexpected SAE occurs at any one site that is determined to be related, probably related or possibly related to study drug, all study sites will be notified by the

Sponsor via the CRO for Study Management and Monitoring and each site will report it to the IRB.

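### Section 8.2 treats class-only serious reactions as unexpected, but Section 8.3.3 and Table 3 call the class risks in Section 1.4.1 expected, so an ocular steroid SUSAR could miss expedited reporting

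*Protocol*

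**What the plan says.** Four places in the protocol bear on expectedness.

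- **Section 8.2 (SUSAR definition).** A serious reaction qualifies if the Brochure does not list it, or does not list it at the observed specificity or severity. It also qualifies if the Brochure mentions it "as occurring with a class of drugs or as anticipated from the pharmacological properties of the study drug, but is not specifically mentioned" for APP13007 itself. The section cross-refers to 8.7.2.
- **Section 8.3.3 (Expectedness).** The first sentence repeats the test of Brochure listing, specificity and severity, without the class clause. The second adds another source: "Expected events for APP13007 administration include those events described in Section 1.4.1", together with the Brochure.
- **Table 3, row on unexpected safety events.** "The list of expected safety events is including in Section 1.4.1", again together with the Brochure.
- **Section 8.7.2 (SUSAR reporting).** It restates *unexpected* against the Brochure by listing, specificity and severity. The class clause is absent. The clocks are set here: 7 calendar days for fatal or life-threatening SUSARs and 15 for all others.

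Section 1.4.1 says of its main ocular list that the active ingredient "has the following anticipated ocular risks associated with the corticosteroid class". A further list of ocular reactions comes from studies of corticosteroids in general after ocular surgery. Section 1.4.2 states: "This is the first time that APP13007 will be administered to humans".

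The note in Section 8.7.1 makes the notice to all sites conditional: "If an unexpected SAE occurs at any one site that is determined to be related". A probable or possible link with the drug also counts.

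**The concern.** A list of class risks is what the last clause of Section 8.2 says does not make an event expected. Section 8.3.3 and Table 3 use such a list to do so. Two safety assessors, each following the protocol, could classify the same event in opposite ways.

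Two consequences depend on that classification: the expedited report to regulators under 8.7.2, and the notice to all sites, with each site's report to its IRB, under the 8.7.1 note. Safety is a primary objective, and Part B adds the 0.1% strength. An event that belongs in the expedited route should not depend on which section the assessor opens.

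**Working it through.** No arithmetic applies. The check is to run one kind of event through each rule.

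**Event.** A serious ocular event that is judged drug-related and described in Section 1.4.1 as a corticosteroid-class risk, such as an ocular infection or a corneal perforation. The outcome depends on what the Brochure says, so all three possibilities are shown. Where the Brochure mentions the event, suppose it does so at the observed specificity and severity.

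| Brochure's treatment of the event | Section 8.2 | Section 8.7.2 | Section 8.3.3 (second sentence) and Table 3 |
|---|---|---|---|
| Mentioned specifically as occurring with APP13007 | Expected | Expected | Expected |
| Mentioned only as a class or anticipated effect | Unexpected | Can be read as expected, because it is listed and no class clause applies | Expected, through 1.4.1 |
| Not mentioned | Unexpected | Unexpected | Expected, through 1.4.1 |

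The rules agree only in the first row. In the second, Section 8.2 says the event "is not specifically mentioned as occurring with the particular drug under investigation" and is therefore a SUSAR, while the other places allow the opposite answer. In the third, Section 8.3.3 also contradicts itself: its first sentence makes the event unexpected and its second makes it expected.

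**Is the second or third row realistic?** APP13007 had not been used in humans when the study began, and Table 3 adds that aqueous clobetasol had not been dosed to the human eye. At that point no ocular class risk could have been listed from human experience with this product. By Amendment 1 about 41 Part A subjects had completed POD15, so that statement describes the start of the study, but Section 1.4.1 still presents these items as class risks.

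**What follows from being called expected:**

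| Step | Depends on expectedness? |
|---|---|
| 7- or 15-day report (8.7.2) | Yes |
| Notice to all sites, then each IRB (8.7.1 note) | Yes |
| SAE report to the sponsor within 24 hours (8.7.1) | No |
| Sponsor's reporting of all SAEs to authorities and ethics committees (8.7.1) | No, but no 7- or 15-day limit is stated there |
| Study-drug stopping steps for IOP, delayed healing, infection, HPA suppression and excess steroid effect (Table 3, Section 9) | No |

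**The case against.** The strongest reply is that the conflict is one of drafting and that other safeguards catch these events. Much of that stands.

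- **Other reporting continues.** A reader might infer that serious steroid harms would go unreported. They would not: every SAE reaches the sponsor within 24 hours and is reported onward. Only the expedited route and the cross-site notice are exposed.
- **Stop-drug review continues.** A reader might also infer that these events escape review of whether study drug should stop. Table 3 has separate rows for the class risks, and Section 9 covers IOP, whatever the expectedness.
- **Section 8.3.3 keeps a specificity and severity test.** Section 1.4.1 ties glaucoma, cataract and bacterial infection to prolonged use, fungal infection to long-term application, and perforation to disease that thins the cornea or sclera. An acute event outside those descriptions could still be unexpected. This narrows the conflict without removing it: the viral-infection entry and the general delayed-healing statement have no such qualifier.
- **Section 8.7.2 does not cite Section 1.4.1.** It should not be read as adopting the 8.3.3 rule. Its defect is the missing class clause. It also requires compliance with a federal regulation and defers procedure to the Safety Management Plan; neither text is in the documents.
- **Table 3 is guidance.** Section 9.1 describes the risk plan that way. Section 8.3.3 is not guidance, and it contradicts 8.2 without help from Table 3.

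**Conclusion.** The inconsistency is in the current text and should be corrected. A serious, drug-related ocular class event can be a SUSAR under Section 8.2 and expected under Section 8.3.3 and Table 3, and so could miss the 7- or 15-day report and the notice to all sites.

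Its size cannot be given as a count. A reader might infer that every class event in Section 1.4.1 changes status between the rules. The documents do not support that, for three reasons. Expectedness under 8.2 turns on the Brochure, which is not available. Some Section 1.4.1 risks come from dermal clobetasol itself, and if the drug under investigation means the active ingredient, they may be expected under either rule. Many of the 23 reactions listed from general corticosteroid studies (9 at 5% to 15%, 4 at 1% to 5%, 10 below 1%) are minor and matter here only if serious. The conflict is clearest for the ocular class risks.

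The conclusion assumes that, for at least one such event, the Brochure is silent or mentions it only as a class or anticipated effect. The documents report no misclassified event.

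**What to change.** 1. Use one definition of expectedness in Sections 8.2, 8.3.3 and 8.7.2 and in Table 3: the Section 8.2 wording, including the class clause.
2. Name one reference document for it, the Investigator's Brochure, and remove Section 1.4.1 as a source of expectedness.
3. Relabel the Section 1.4.1 list as anticipated risks for investigator awareness, and state that appearing there does not by itself make an event expected for reporting.
4. Align the Safety Management Plan.
5. If any serious related event has been classed as expected under the current 8.3.3 or Table 3 wording, re-check that call.

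The cost is wording in a few protocol sections and one companion plan, with possibly a few more expedited reports. No dose, visit, endpoint or analysis changes.
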